### **COVID-19 Procedures**

Due to the COVID-19 pandemic, the remainder of participants will be recruited and enrolled virtually. We will be utilizing social media for recruitment and zoom to complete the enrollment visit. Recruiters will screen potential recruits over the phone and if eligible, set up a zoom meeting for enrollment. Participants will be consented with the oral consent script. The recruiters will read the baseline ACASI to the participants and record their answers. There will be separate zoom meeting for the individual gender-matched intervention and if the participants are randomized to the

intervention group, they will join after for the joint-debrief session. The exit survey through Qualtrics will be read to the participants afterwards by the recruiters and record their answers.

Gift cards will be mailed to the participants after the enrollment visit has been completed.

The 6-8 follow-up survey will remain the same and be completed over the phone with the participant.

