##### Participants and Recruitment:

Fifty dyads will be recruited from Johns Hopkins primary and affiliated institutions in the greater Baltimore metropolitan area. Index participants engaged in heterosexual relationships will be asked to recruit their main partner for enrollment in the dyadic intervention pilot. The index participant and their partner will contact study staff to be scheduled for a research visit together. Our target is to have complete data on 40 dyads so we set sample size at 50 in order to account for attrition. However, we will stop recruiting when we reach 40 participants.

**Enrollment, Consent, Randomization, and Treatment:** Recruiters will be available via phone during office and some evening hours for the Title X clinical setting. Providers for study contact will refer patients. Patients who agree to be contacted will be approached by a recruiter in person-or via phone and if eligible, the dyad will be scheduled for written informed consent and intervention procedures. At enrollment, the research staff will perform a detailed review of the EXPERIENCE

study with informed consent. While the index patient and their partner are required to present together for study enrollment, they will each be consented separately. Participants will have the option to separately consent for 1) completing both the ACASI and dyadic intervention and 2) additionally completing an in-depth interview. All study protocol study forms will be faxed to the project director at the time of enrollment and online questionnaire/ interview will be automatically uploaded to a secure server for warehousing in a central database. After enrollment, participants will be assigned to the control (1) versus intervention (2) using a computer generated randomization assignment. Envelopes based on dyadic study group number will be available to the research staff at the time of enrollment to adhere to the randomization sequence.

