## 7. Study Statistics

- a. Primary outcome variable. The primary outcome variable for this pilot study is feasibility of recruitment. Recruitment feasibility will be defined as the number of dyads completing the intervention out of number of eligible dyads. The feasibility of short-term retention will be calculated as the proportion of enrolled participants, who complete a follow-up interview at 6 weeks.
- b. Secondary outcome variables. The secondary outcome variable for this pilot study is acceptability, measured as participant satisfaction with their intervention experience. Participant satisfaction will be measured using a brief survey asking participants to rate their experience and qualitative feedback documented.
- c. Statistical plan including sample size justification and interim data analysis.

We will enroll a total of 50 adolescent dyads. While the choice of 50 dyads is inherently arbitrary, it is the number we feel we can realistically enroll within our limited time of this pilot study. While we won't have power to detect statistically significant differences, we will be able to examine correlations, which will be informative for future research proposals. To address each aim, we will evaluate our outcomes, feasibility and acceptability, against benchmarks from previous studies. To address aim 1, we will compare observed recruitment rates from the proposed pilot study to expected recruitment rates. Expected recruitment rates will be determined from previous studies that recruited adolescents with an STI diagnosis. Prior studies recruiting from the Adolescent Medicine Clinic have achieved recruitment rates ranging from 48 to 91%. To address aim 2, we will use a similar approach, comparing satisfaction scores to an a priori benchmark of patient satisfaction. Based on previous work, average patient satisfaction greater than 80% would be necessary to conclude that the intervention is acceptable.

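### Recruitment moves from clinic referral to social media and Zoom mid-study, but Section 7 keeps one recruitment ratio and a clinic-derived benchmark, with no reporting by phase

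*Combined protocol and SAP*

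**What the plan says.** Under Participants and Recruitment, the source is institutional: "Fifty dyads will be recruited from Johns Hopkins primary and affiliated institutions in the greater Baltimore metropolitan area". Providers refer patients, and "Patients who agree to be contacted will be approached by a recruiter in person-or via phone". The index patient and partner must attend enrolment together.

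The COVID-19 Procedures section then states that "the remainder of participants will be recruited and enrolled virtually", and adds: "We will be utilizing social media for recruitment and zoom to complete the enrollment visit". Screening is by phone, consent is oral, and sessions are held on Zoom. Recruiters read out the baseline and exit surveys and record the answers. The follow-up survey at 6 to 8 weeks is unchanged and is done by phone.

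Section 7a gives one primary definition: "Recruitment feasibility will be defined as the number of dyads completing the intervention out of number of eligible dyads". Section 7c gives the comparison: "To address aim 1, we will compare observed recruitment rates from the proposed pilot study to expected recruitment rates". The expected rates have a stated origin: "Expected recruitment rates will be determined from previous studies that recruited adolescents with an STI diagnosis", and "Prior studies recruiting from the Adolescent Medicine Clinic have achieved recruitment rates ranging from 48 to 91" percent. Section 7c also requires average satisfaction above 80% before the intervention is called acceptable.

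Section 7 has no split by period, source or visit mode, and no benchmark for social-media recruitment. Its only COVID-related text covers the separate outreach survey.

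**The concern.** Recruitment feasibility is the primary outcome. After the switch, the ratio in Section 7a covers two different recruitment processes, while its comparator comes from one clinic. Followed as written, the plan sets social-media recruits against a clinic benchmark and produces one number for both routes.

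That number could fall inside the benchmark range although one route recruited poorly, or below it although clinic recruitment was satisfactory. A later trial has to choose a recruitment route, and a single figure does not show which one worked.

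Satisfaction raises a smaller, related issue. In the virtual phase the exit survey is answered aloud to study staff, which may change the scores that are judged against 80%.

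**Working it through.** **Inputs from the documents**
- Primary ratio: completing dyads / eligible dyads (Section 7a).
- Benchmark: 48 to 91%, Adolescent Medicine Clinic (Section 7c).
- Target of 40 dyads with complete data out of 50 enrolled (Participants and Recruitment).
- Number of dyads in each phase and recruitment rate in each phase: not given.

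**The plan's own figure.** 40/(1 − 0.20) = 50. The 20% is back-calculated from 40/50, since no attrition rate is stated. The match therefore shows only that the two numbers are consistent. There is no power calculation to reproduce.

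**How wide the benchmark is.** With 40 completing dyads, the eligible denominators that fall inside the range run from 40/0.91 = 43.96 to 40/0.48 = 83.3, that is, any count from 44 to 83.

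**How a single ratio combines two phases.** With f the virtual share of eligible dyads:

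overall rate = (1 − f) × clinic rate + f × virtual rate

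Assumed rates (rows) and overall rate by virtual share (columns):

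| Clinic / virtual rate | f = 10% | 25% | 50% | 75% |
|---|---|---|---|---|
| 70% / 50% | 68% | 65% | 60% | 55% |
| 70% / 30% | 66% | 60% | 50% | 40% |
| 70% / 20% | 65% | 58% | 45% | 33% |
| 60% / 60% | 60% | 60% | 60% | 60% |

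At 70% and 30%, the overall rate stays at or above 48% until f = (0.70 − 0.48)/(0.70 − 0.30) = 0.55. When the rates are equal, combining the phases does no harm.

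**Illustrative counts** (40 completing dyads in total; the splits are assumed; exact Clopper-Pearson 95% intervals):

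| Scenario | Clinic | Virtual | Overall |
|---|---|---|---|
| A | 12/40 = 30% (17–47) | 28/35 = 80% (63–92) | 40/75 = 53% (41–65) |
| B | 30/43 = 70% (54–83) | 10/33 = 30% (16–49) | 40/76 = 53% (41–64) |
| C | 20/29 = 69% (49–85) | 20/67 = 30% (19–42) | 40/96 = 42% (32–52) |

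A and B give nearly the same overall rate from opposite situations. In C the overall rate lies below the range although the clinic rate lies inside it.

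**The case against.** Several points on the other side are sound.

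- **Combining the phases is inferred.** No sentence says they will be pooled, and Section 7c speaks of observed rates in the plural. What the text supports is one unstratified definition and silence on phase. A reader might infer that the overall figure must describe neither setting. That does not follow: at 70% and 30% with a 10% virtual share, the overall 66% is close to the clinic rate, and with equal rates nothing is lost.
- **Both routes involve self-selection.** Clinic patients were also filtered, by referral and by agreeing to be contacted, and Section 5 requires willingness to recruit the partner in every case. The degree of selection may differ, but it is not confined to social media.
- **The benchmark was loose before the switch.** It is described as coming from studies of adolescents in one clinic, whereas the outcome counts dyads, and the Setting paragraph allows referrals from several sites. Section 7c also sets no pass mark, so 48% is the lower end of past rates and not a stated cut-off.
- **The illustrations are fragile.** In scenario A, one more completing clinic dyad gives 13/40, with an interval of 18.6 to 49.1% that is no longer wholly below 48%.
- **Retention and the arm comparison.** A reader might infer that the switch also changes how retention is measured, or biases Objective 3. The documents do not support either inference. Follow-up by telephone was already planned and stays the same. Dyads are randomised in both phases, so phase is not a systematic confounder. Section 7 specifies no Objective 3 model and disclaims power, so a phase covariate would be a matter of preference.
- **The data are recoverable.** The recruitment screener logs ineligibility and refusal, and phase follows from the date.

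These points limit the claim without removing it. The last one shows that the remedy is cheap; it does not show that the plan already contains it.

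**Conclusion.** The concern holds in a limited form. Source and visit mode change for all remaining dyads, and the primary recruitment ratio and its benchmark were left as they were. If the phases recruit at different rates, the single figure may misstate feasibility for either route. How far cannot be determined from the documents, because the split and both rates are missing. In the assumed cases with a 70% clinic rate and a 30% virtual rate, the overall rate runs from 66% at a 10% virtual share to 40% at 75%. With equal rates there is no distortion. The data stay usable and the gap can be closed at the reporting stage, so this is an inexpensive improvement to the primary analysis and not a flaw that invalidates the pilot.

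**What to change.** In Section 7:

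1. Report the numbers of eligible, enrolled and completing dyads, and the recruitment ratio with an exact 95% confidence interval, separately for the clinic-referred phase and the social-media/Zoom phase.
2. Compare only the clinic-referred rate with 48 to 91%. State that this benchmark reflects individual adolescents from one clinic and is approximate for dyads from several sites. Report the virtual rate descriptively, without a benchmark.
3. Show satisfaction by phase, because the exit survey becomes recruiter-read.

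No phase term is needed for Objective 3, and retention measurement needs no change on this account.

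The cost is a phase indicator and a few extra table columns, with no new data and no larger sample. The downside is precision: in scenario B, the interval is 41 to 64% for all 76 eligible dyads, but 54 to 83% for the 43 clinic dyads and 16 to 49% for the 33 virtual dyads.

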### **In-depth Interviews**

For a subset of participants, we will conduct separate in-depth, semi-structured, face-to-face and/or via telephone interviews. Participants for the interview will either be 1) enrolled in the EXPERIENCE study intervention and agree to the additional and optional in depth interview or 2) agree to participate in an in depth interview only and not enrolled in the intervention. The interview will explore the social context, specifically social support; relationship qualities, modeling, and communication; and communal coping, that informs AYA partner-dyad's sexual health individually and at the partner level. For those participants that are enrolled in the intervention: the interview will occur 6-8 weeks after the dyad has completed the intervention. For those participants agreeing to an in depth interview only: the interview will be scheduled after written consent is completed. Participants will also be asked to complete a brief demographic questionnaire. We anticipate 40 individual interviews, but will continue sampling until we reach data saturation. The interviews for female and male partners will be conducted separately as to avoid any bias or influence of partner presence in given responses. An in-depth interview guide has been developed for the individual interviews. The semi-structured interview guide focuses on obtaining AYA perceptions of how social context informs sexual health. The concepts of sexual health that will be explored will include sexual experiences, partnering decisions, sexual communication, and prevention of STIs. The development of the interview guide will be an iterative process, which will allow additional questions to be added to the interview guide as necessary. Using the interview guide, the interviewer will ask open-ended questions and seek clarification or elaborations as necessary. All sessions will be audio-recorded and the interviewer will take written notes during and after each interview. During the interview, the interviewee will be asked to refer to themselves, partner(s), and/or other individuals only by an initial to protect confidentiality on recorded audio. Participants who complete the in-depth interview will receive \$50 in remuneration.

### **COVID-19 Survey**

We will conduct outreach regarding COVID-19 via phone. Questions will include basic information about living conditions, sexual behavior, relationship status, and SRH behaviors and healthcare needs since the stay-at-home order [March 16, 2019 (school closings)] through the present. We will interview individuals at baseline and three months from their designated call to determine if there is any change in behavior or circumstance [attached].

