### **To evaluate the impact of the COVID-19 stay-at home orders on TECH-N participants' SRH behaviors and risk for STI.**

**Hypothesis 1:** AYA with a greater number of psychosocial risk factors across housing, food insecurity, income, and social support will have greater engagement in sexual risk-taking behaviors (e.g. non-condom use, non-use of contraception) during the COVID-19 stay at home order.

**Hypothesis 2:** AYA with reduced SRH risk-taking behaviors during the COVID-19 stay at home orders are more likely to engage in increased SRH risk-taking behaviors once the order has been lifted.

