### **Quality Control**

**1. Treatment Fidelity:** Drs. [name] and [name] [with technical assistance [TA] for specific interventions] will train and supervise research staff to ensure protocol execution with dyads.

**2. Recruitment Screener:** Includes collection of basic demographic data and the outcome of recruitment effort so that we can keep an accurate account of referral patients who are ineligible and/or refuse to participate in the intervention. We include a standard question about (intimate partner violence) IPV in the screener to determine if this is a reason for refusal and/or influence the communication/behavior in the relationship over time. Participants who screen positively, will be provided with information and resources about IPV in the individual visit and referrals placed to the primary health provider for additional services.

**3. Surveys:** We have developed a survey to collect sexual and reproductive health history, perceived barriers to treatment, and self-efficacy data to be administered online during the study visit. This interview will be modified for this study, but will include: demographics, reproductive and sexual history (# partners, partner status (main versus casual), relationship status, coital frequency, prior STIs, condom use consistency, contraceptive use preferences for partner notification (e.g. female partner notification, case worker notification, email, text message), emotional response to diagnosis, access to medical care, access to technology (phone, internet, text), social provisions scale, and the short-form survey instrument (SF-12) as a measure of health-related quality of life, Fertility Knowledge and Awareness Scale, clinical symptoms, sensation seeking scale, relationship qualities scale and intimate disclosure scales to measure relationship quality and dyad communication, childbearing motivation and communal coping. We will also query patients at the end of the intervention to determine their level of confidence for negotiating with their partner and their satisfaction with the experience. It is important to test these measures with participants and the timing of completion.

Participants will be contacted in 6-8 weeks for a brief (~30 min) telephone (or in-person) follow-up interview to assess sexual risk-taking behaviors, relationship status, social support, and satisfaction with the intervention experience.

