#### COVID-19 Outreach Study

Descriptive and bivariate analyses will be performed to determine the general impact of COVID-19 risk on AYA in the sample and to evaluate the covariates such as change in living situation, cohabitation, stress, access to SRH services and COVID-fears on SRH behaviors.

Bivariate analyses generating  $p \leq 0.1$  will be evaluated using logistic regression models, accounting for potential confounders or effect modifiers.

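### The COVID-19 survey's recall period ends on the day of the call, so any-event and count answers mix behaviour with time at risk, blur during and after the order, and cannot show change if the second call repeats the question

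*Combined protocol and SAP*

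**What the plan says.** In section 4, the COVID-19 Survey paragraph sets the recall period: questions cover "SRH behaviors and healthcare needs since the stay-at-home order [March 16, 2019 (school closings)] through the present". It then gives the schedule: "We will interview individuals at baseline and three months from their designated call to determine if there is any change in behavior or circumstance". Both calls are timed person by person. No common calendar date and no fixed look-back length is stated. The questionnaire is marked as attached and is not in the text.

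The two COVID-19 hypotheses in section 2 refer to different periods. Hypothesis 1 takes a count of psychosocial problems as its exposure and predicts that people with more of them "will have greater engagement in sexual risk-taking behaviors (e.g. non-condom use, non-use of contraception) during the COVID-19 stay at home order". Under Hypothesis 2, people whose risk-taking fell during the order "are more likely to engage in increased SRH risk-taking behaviors once the order has been lifted". No end date for the order is given.

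In section 7, the COVID-19 Outreach Study paragraph plans descriptive and bivariate analyses to "evaluate the covariates such as change in living situation, cohabitation, stress, access to SRH services and COVID-fears on SRH behaviors". Associations with p of 0.1 or less then "will be evaluated using logistic regression models, accounting for potential confounders or effect modifiers". Call date, recall length, an offset and person-time are not mentioned, and the coding of the behaviour outcomes is not defined.

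**The concern.** A period with a fixed start and a moving end gives each participant a different time at risk. Someone reached two months after the start reports on two months, and someone reached after five reports on five. If the answer is coded as any occurrence or as a count, it grows with the period even when behaviour is constant. Three things are at stake.

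- **Description.** Any-event prevalences depend on when the calls happened to be made.
- **Change between calls.** If the second call again asks about everything since the order, its window contains the first one. An accurate yes cannot become a no, so the proportion can rise but not fall.
- **The hypotheses.** One open window does not separate the order from its aftermath, which is the contrast in Hypothesis 2. For Hypothesis 1, problems with housing or income could plausibly delay telephone contact. The longer window would then fall on the more exposed people, in the direction that the hypothesis predicts.

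**Working it through.** The documents give no sample size, event rate, spread of call dates or expected effect for this survey, so there is no figure to reproduce. All rates, delays and sample sizes below are assumptions.

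**1. Recall length and an any-event answer.** With the same independent monthly chance p for everyone, P(any event in t months) = 1 − (1 − p)^t. At p = 0.25:

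| Months | P(any) | Odds ratio against 2 months |
|---|---|---|
| 2 | 1 − 0.75² = 44% | 1 |
| 3 | 1 − 0.75³ = 58% | 1.8 |
| 4 | 1 − 0.75⁴ = 68% | 2.8 |
| 5 | 1 − 0.75⁵ = 76% | 4.1 |

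Condom and contraceptive habits are likely to persist within a person, which weakens the effect. If the monthly chance varies between people as Beta(0.25, 0.75), the mean is still 25%, and P(no event in t months) is the product of (0.75 + j)/(1 + j) for j = 0 to t − 1. For 2 months this is 0.75 × 1.75/2 = 0.656, so 34% report an event; for 5 months it is 0.536, so 46% do. The odds ratios at 3, 4 and 5 months fall to 1.3, 1.5 and 1.7.

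**2. Effect on Hypothesis 1 when there is no true association.** Simulation with 2,000 runs per setting: risk-factor count from Binomial(4, 0.4); recall length = 1.5 + Exponential(mean 1) + slope × count, in months; any-event outcome; logistic regression on the count. Percentage significant at 0.05 (repeat runs differ by a point or two):

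| Setting | n = 80 | n = 150 | n = 250 |
|---|---|---|---|
| Same chance, half a month per factor | 16 | 29 | 43 |
| Same chance, quarter of a month per factor | 8 | 12 | 17 |
| Chance varies, Beta(0.5, 1.5), half a month | 8 | 11 | 15 |
| Chance varies, Beta(0.25, 0.75), half a month | 7 | 8 | 9 |
| No link between count and delay | about 5 | about 5 | about 5 |
| Common end date (2-month window for all) | 4–5 | 4–5 | 4–5 |

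In the first setting, 26%, 41% and 56% pass the 0.1 screen. Adding log recall length as a covariate there returns the rate at 0.05 to 4–6%; at n = 150, a log-length offset brings it from 29% to 6%.

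A second model agrees. It uses a constant rate r of 0.1 to 0.4 per month, P(any) = 1 − exp(−rt), and a binary risk factor that delays the call by one month. The 0.1 screen is passed in 18% to 29% of surveys at n = 80 and 30% to 52% at n = 200. With no delay link the figure is about 10%, and with one fixed look-back for all it is 9.4% to 10.8%.

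**3. The second call.** At r = 0.1 per month, a first call at 2 months gives 1 − exp(−0.2) = 18.1%. A second call three months later that asks again from the order gives 1 − exp(−0.5) = 39.3%. Behaviour has not changed.

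**The case against.** The strongest reply is that the instrument cannot be seen. The survey paragraph summarises topics; the attached questionnaire may set narrower periods. Outcomes may also be of a kind that does not accumulate. The main study survey includes "coital frequency, prior STIs, condom use consistency", and condom consistency, like current contraceptive use, does not rise mechanically with recall length. This stands, and it limits the point to any-event and count items.

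Second, Hypothesis 1 is worded for behaviour during the order. If the items follow that wording, the window closes when the order ends and is the same for everyone called afterwards; the simulation then shows no inflation. This also stands. But the survey paragraph runs to the day of the call, and nothing says when the calls fall relative to the end of the order.

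Third, a reader might infer that people who are harder to reach will look riskier and that Hypothesis 1 is therefore biased in its own favour. The documents do not support that. They say nothing about call order, contact attempts or the spread of call dates for this survey, so the link between risk factors and delay is conjecture. Without it, the error rate is nominal.

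Fourth, the covariate list is illustrative and the models allow for unspecified confounders, so recall length could be added without departing from the plan. That is true, but nothing commits the study to recording or using it, and answers given for an open window cannot be divided afterwards.

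Finally, this is an add-on survey, and the trial's primary and secondary outcomes are untouched.

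**Conclusion.** The point holds in limited form. As written, the recall length depends on the call date, the order and its aftermath are not separated although the two hypotheses need them to be, and no adjustment for length is named. For any-event and count items, prevalences then depend on call date, and a repeated question at the second call cannot show change. Neither consequence needs a link between risk factors and delay.

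Bias in Hypothesis 1 is conditional. It needs an accumulating outcome, call delay related to the risk factors, and a window not closed at the end of the order; the documents establish none of the three. If all hold, with half a month of delay per factor, a 25% mean monthly chance and 80 to 250 people, false significance at 0.05 is about 16% to 44% when the chance is the same for all and about 7% to 16% when it varies. The lower range is the more realistic if habits persist. Without a delay link, or with a common end date, it is about 5%. The change is worth making because it is nearly free and the loss cannot be repaired after the calls.

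**What to change.** In the COVID-19 Survey section:

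- Record the date of every call.
- Ask about the order period, with the same stated start and end dates for everyone, separately from the period after it was lifted. Check the printed year of the start date at the same time; an error there shifts every window equally and does not affect the comparison between people.
- Have the second call ask only about the time since the first call, or use the same look-back length at both calls. A short look-back ending at the call should not replace the order-period question, because it can miss the order entirely for people called later.

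In the COVID-19 Outreach Study paragraph:

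- State how each behaviour outcome is coded.
- For any any-event or count item whose period still varies, include log recall length, either as an offset with a complementary log-log link (any event) or a log link (count), or as a covariate. The offset assumes a constant rate over the period. The covariate does not fix the coefficient at 1, so it is safer if behaviour varies widely between people.

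The cost is slightly longer question wording, one derived variable, and fewer reported events where the period becomes shorter.
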